8.2 Responsibility for Analyses/In-House Blinding

The statistical analyses of the data obtained from this study will be the responsibility of the Clinical Biostatistics department of the Sponsor.

The trial is open-label (ie, subjects, investigators, and Sponsor personnel will be aware of subject treatment assignment after each subject is enrolled and treatment is assigned). Allocation to treatment will not be randomized.

8.3 Hypotheses/Estimation

Objectives and hypotheses of the study are outlined in Section 3.0.

8.4 Analysis Endpoints

8.4.1 Efficacy/Immunogenicity/Pharmacokinetic Endpoints

Efficacy endpoints are secondary and exploratory endpoints in this study (refer to Sections 3.2 and 3.3).

The following efficacy endpoints are derived from the RECIST 1.1 criteria:

Objective Response Rate: defined as the proportion of subjects who have achieved confirmed CR or PR.

Duration of Response: defined for subjects who achieved a tumor response (CR or PR) as the time between the date of the first documented tumor response and the subsequent date of the objectively documented disease progression or death, whichever occurs first. Response duration for subjects who have not progressed or died at the time of analysis will be censored at the date of their last tumor assessment.

Disease Control Rate: defined as the proportion of subjects who have achieved CR, PR, or SD.

Progression-free Survival: defined as the time from the first dose of study medication to the first objective documentation of tumor progression or death due to any cause. Detailed censoring rules will be described in the sSAP.

Overall survival: defined as the time from the first dose of study medication to death due to any cause. Subjects who did not die will be censored on the date of their last study assessment or contact.

PK endpoints include serum concentrations of MK-8353 and pembrolizumab and derived PK parameters.

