5.8.1.1 Discontinuation of Trial Treatment After Disease Response

Subjects who attain an investigator-determined confirmed disease response of complete response (CR) may discontinue study treatment (MK-8353 and pembrolizumab) after receiving at least 2 additional cycles of MK-8353 and pembrolizumab, as applicable, beyond the date when the initial response was declared and after a total of at least 8 cycles of MK-8353 and pembrolizumab, as applicable. The decision to continue or discontinue study treatment after confirmed disease response is at the investigator's discretion.

After treatment discontinuation, each subject will be followed for 30 days for AE monitoring. Subjects will be monitored for SAEs for 90 days after treatment discontinuation, 30 days if the subject initiates new anticancer therapy less than 30 days after study treatment discontinuation, or the day new anticancer therapy is initiated if between 30 days and 90 days after study treatment discontinuation. Subjects with an ongoing AE of Grade >1 at the time of treatment discontinuation will be followed until resolution of the AE to Grade 0 to 1, until considered stable by the treating physician, or until beginning a new anticancer therapy, whichever occurs first.

Subjects will have posttreatment follow up for disease status until disease progression, initiating a new anticancer therapy, withdrawing consent for study participation, or becoming lost to follow up.

After confirmed disease progression each subject will be contacted by telephone approximately every 12 weeks (84 \pm 7 days) for survival until withdrawal of consent to participate in the study, becoming lost to follow up, death, or end of the study, whichever occurs first.

Subjects who discontinue study treatment after confirmed CR may be eligible to be re-treated with study treatment at the discretion of the investigator, if all of the following conditions are met:

- The subject experiences investigator-determined confirmed disease progression;
- No other anticancer therapy was administered since the last dose of study treatment;
- The subject meets the safety parameters listed in the Inclusion/Exclusion criteria; and
- The study is ongoing.

Subjects will resume study treatment in the same Part of the study and at the same dose of MK-8353 to which they were initially allocated and at the 200 mg fixed dose of pembrolizumab. The criteria for withdrawal and discontinuation after re-treatment are as

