10. AEs and SAEs will be recorded from the time of treatment allocation. All AEs and SAEs that occur after the consent form is signed but before treatment allocation must be reported by the investigator if they cause the subject to be excluded from the trial, or are the result of a protocol specified intervention, including but not limited to washout or discontinuation of usual therapy or a study procedure. After treatment discontinuation, each subject will be followed for 30 days for AE monitoring. Subjects will be monitored for SAEs for 90 days after treatment discontinuation, 30 days if the subject initiates new anticancer therapy less than 30 days after study treatment discontinuation, or until the day new anticancer therapy is initiated if between 30 days and 90 days after study treatment discontinuation. Subjects with an ongoing AE of

Grade >1 at the time of treatment discontinuation will be followed until resolution of the AE to Grade 0 to 1, until considered stable by the treating physician, or until beginning a new anticancer therapy, whichever occurs first.

11. Baseline radiology scans of chest, abdomen, and pelvis, and all known tumor sites (if evaluable by imaging) must be obtained within 28 days prior to C1D1 and must be repeated every 9 weeks (± 7 days) from C1D1. Confirmatory scans to confirm progressive disease should be obtained at least 4 to 5 weeks after the documented response. Imaging must be obtained at the End of Treatment Visit at discontinuation unless done within the previous 4 weeks. Imaging is to be continued if subject discontinues study for reason other than progressive disease.
12. After confirmed disease progression, subjects will be contacted by telephone approximately every 12 weeks for survival until withdrawal of consent to participate in the study, becoming lost to follow up, death, or end of the study, whichever occurs first. Updated survival status may be requested by the Sponsor at any time during the course of the study. Upon Sponsor notification, all subjects who do not/will not have a scheduled study visit or study contact during the Sponsor defined time period will be contacted for their survival status (excluding participants that have a death event previously recorded).

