11. Baseline radiology scans of chest, abdomen, and pelvis, and all known tumor sites (if evaluable by imaging) must be obtained within 28 days prior to C1D1 and must be repeated every 9 weeks (\pm 7 days) from C1D1. Confirmatory scans to confirm PD should be obtained at least 4 to 5 weeks after the documented response. Imaging must be obtained at the End of Treatment visit at discontinuation unless done within the previous 4 weeks. Imaging is to be continued if subject discontinues study for reason other than PD.
12. After confirmed disease progression each subject will be contacted by telephone approximately every 12 weeks for survival until withdrawal of consent to participate in the study, becoming lost to follow up, death, or end of the study, whichever occurs first. Updated survival status may be requested by the Sponsor at any time during the course of the study. Upon Sponsor notification, all subjects who do not/will not have a scheduled study visit or study contact during the Sponsor defined time period will be contacted for their survival status (excluding participants that have a death event previously recorded).
13. Tumor tissue (archival or newly obtained biopsy) will be required at Screening upon signing the informed consent for the study. This sample will be assessed to collect information on the RAS/RAF and pMMR/dMMR (MSI) tumor mutation status and exploratory biomarkers for all subjects enrolled in the study. Sample can be evaluated for mutation by local laboratory testing, or sent to central laboratory for analysis (if cannot be performed by local laboratory). Tissue will be also sent to central laboratory for biomarker analysis and leftover tissue may be saved for FBR if the subject signs the FBR consent.
14. This sample should be drawn for planned analysis of the association between genetic variants in DNA and drug response. This sample will not be collected at that site if there is either a local law or regulation prohibiting collection, or if the IRB/IEC does not approve the collection of the sample for these purposes. If the sample is collected, leftover extracted DNA will be stored for future biomedical research if the subject signs the FBR consent. If the planned genetic analyses are not approved, but FBR is approved and consent is given, this sample will be collected for the purpose of FBR.

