7.1.2.6 Disease Assessments

Response will be based on RECIST 1.1 (Appendix 12.4) as assessed by investigator/local radiology review. Images used for tumor measurements will be sent to a central imaging vendor for potential blinded, central review. The process for image collection and transmission to the central imaging vendor can be found in the SIM.

Immunotherapeutic agents, such as pembrolizumab, may produce antitumor effects by potentiating an endogenous cancer-specific immune response. The response patterns seen with such an approach may extend beyond the usual time course of responses seen with typical cytotoxic agents, and can manifest a clinical response after an initial increase in tumor burden or even the appearance of new lesions. Subjects could, at the discretion of the investigator, continue in the trial until the initial assessment of progressive disease is confirmed at least 4 weeks later (refer to Section 4.2.3.1). The details on the irRECIST assessment can be found in Appendix 12.5.

Initial imaging (eg, CT scan, MRI, positron emission tomography) should be performed within 28 days prior to the first dose of study treatment, and should be repeated 9 weeks after the first dose and every 9 weeks until confirmed progressive disease, initiating a new anticancer therapy, withdrawing consent for study participation, or becoming lost to follow up, whichever occurs first.

The same imaging technique should be used at each time point and the schedule of disease assessment should not be adjusted for delays, if any, in cycle starts.

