8.6 Statistical Methods

This section describes the statistical methods that address the primary and secondary objectives. Methods related to exploratory endpoints will be described in the sSAP.

PK will be analyzed and reported separately.

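### ORR counts only confirmed responses but DOR is defined for any CR or PR, so the DOR set can include subjects whom ORR counts as non-responders

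*Combined protocol and SAP*

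**What the plan says.** Section 8.4.1 gives the efficacy definitions one after another. ORR is "defined as the proportion of subjects who have achieved confirmed CR or PR". DOR, which comes next, is "defined for subjects who achieved a tumor response (CR or PR) as the time between the date of the first documented tumor response" and the later date of documented progression or death. Subjects without either event are censored at their last tumor assessment. ORR is the key secondary endpoint (Section 8.1); DOR is exploratory (Sections 3.3 and 4.2.3.1).

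On imaging, Section 7.1.2.6 says "Response will be based on RECIST 1.1 (Appendix 12.4) as assessed by investigator/local radiology review" and that scans "should be repeated 9 weeks after the first dose and every 9 weeks until confirmed progressive disease". It gives no separate scan or minimum interval for confirming a CR or PR. Section 5.8.1.1 also relies on confirmation ("Subjects who attain an investigator-determined confirmed disease response of complete response (CR) may discontinue study treatment") without describing how it is obtained.

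The only confirmatory scan in the flow charts is in note 11. For Arms A to C and Part 2 it reads: "Confirmatory scans to confirm progressive disease should be obtained at least 4 to 5 weeks after the documented response". For Arm D it reads: "Confirmatory scans to confirm PD should be obtained at least 4 to 5 weeks after the documented response".

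Section 8.6 adds: "Methods related to exploratory endpoints will be described in the sSAP".

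**The concern.** DOR will normally be read beside ORR as the duration of the responses that ORR counts. As worded, it need not be. The ORR line shows that the authors distinguish confirmed from unconfirmed response, so a programmer working from the next definition has no licence to supply the missing word. Followed literally, the DOR rule admits responses that ORR rejects. Those are likely to be among the shortest, because a response often goes unconfirmed when the next scan shows progression. With the 4 to 10 responders that Table 11 contemplates, a few such subjects could move a median noticeably.

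Note 11 might have been expected to settle how a response is confirmed. It does not: its stated purpose is to confirm progression, but its clock starts at a response.

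**Working it through.** **Figures in the plan.** The plan states no figure for DOR. The nearby figures concern ORR and do not depend on the DOR definition. The futility figure is 1 − 0.9^18 = 0.850, against 85% stated. Of the 14 Clopper-Pearson rows in Table 11, 12 reproduce to one decimal. The other two differ by 0.1 point in the upper limit (8/40: 35.6% against 35.7% printed; 9/40: 38.5% against 38.4%). None of these changes under the fix.

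**The two definitions applied to one subject** (scans at weeks 9, 18, 27):

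| Scans | ORR | DOR as worded |
|---|---|---|
| PR at 9, PD at 18 | non-responder (never confirmed) | 18 − 9 = 9 weeks |
| PR at 9, PR at 18, PD at 27 | responder | 27 − 9 = 18 weeks |

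Every ORR responder is in the DOR set. The DOR set is larger by the number k of subjects whose CR or PR is never confirmed. If k = 0 the sets are identical.

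**Share of the DOR set outside the ORR numerator.** With 6 confirmed responders (assumed; 6/40 is the 15% row of Table 11), the share is k/(6 + k): 0%, 14.3%, 25%, 33.3% and 40% for k = 0, 1, 2, 3 and 4.

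**Why the median moves.** Suppose every unconfirmed duration is shorter than every confirmed one. In terms of the 6 ordered confirmed durations, the sample median of the 6 + k values is:

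- k = 0: the mean of the 3rd and 4th
- k = 1: the 3rd
- k = 2: the mean of the 2nd and 3rd
- k = 3: the 2nd
- k = 4: the mean of the 1st and 2nd

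**Illustration in weeks.** Assumed inputs: 6 confirmed responders; exponential time T with median 39 or 26 weeks; confirmed DOR = max(18, 9 × ⌈T/9⌉), that is, 9-weekly scans with the 18-week minimum shown above; k unconfirmed responders, each with DOR of 9 weeks; no censoring. Mean of the sample median over simulated sets:

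| Underlying median | k = 0 | 1 | 2 | 3 | 4 |
|---|---|---|---|---|---|
| 39 weeks | 49 | 40 | 33 | 27 | 24 |
| 26 weeks | 34 | 29 | 25 | 22 | 20 |

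The k = 0 values lie above the underlying medians because of rounding up to the scan grid and the 18-week floor. The comparison that matters is along each row.

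**Note 11 beside the other text.** Sections 2.1 and 7.1.2.6 and Table 13 count at least 4 weeks from the first evidence of progression. Note 11 counts at least 4 to 5 weeks from the documented response. The starting points differ, so the texts do not agree.

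**The case against.** The strongest reply is that DOR directly follows ORR, so its tumor response may be shorthand for the response just defined. Dating from first documentation is compatible with a confirmed-only DOR. On this view a word was left out and nobody chose to count unconfirmed responses. That may well be the intent, but the text does not say so, and the remedy is the same.

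A second reply is that DOR is exploratory and its methods go to the supplemental SAP, which is not among the documents and may restrict the set. This limits what can be said about the eventual analysis. It does not remove the inconsistency: the DOR definition, with its censoring, is printed in Section 8.4.1, where only the PFS censoring rules are expressly deferred.

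Third, the illustration depends on its inputs. The documents give neither an unconfirmed-response rate nor a DOR median. If an unconfirmed responder has no further scan and does not die, Section 8.4.1 censors at the last assessment, and the pull on the median is smaller. At k = 0 there is no effect. All of this stands.

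A reader might also draw three stronger inferences that the documents do not support:

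- **That ORR and DOR describe different responders.** The sets are nested, so they can differ but need not.
- **That response cannot be confirmed, or will be confirmed differently from site to site, because no confirmatory scan is set for it.** The next 9-weekly scan can serve. What is missing is a statement saying so, and between-site variation is conjecture.
- **That ORR itself could be inflated, for example from 6/40 to 9/40.** Unconfirmed responses never enter ORR as defined.

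**Conclusion.** The point holds as an inconsistency between two adjacent definitions. As written, DOR can include subjects whom ORR counts as non-responders, and the sets coincide only if every response is confirmed. The effect on median DOR runs from none to, in the most extreme case shown, about half (49 to 24 weeks with 4 unconfirmed responders added to 6 confirmed). That end of the range rests wholly on the assumed counts, the assumed medians, progression at the next scan and no censoring; it is not a prediction. The ORR definition, the sample size, Table 11 and the futility figure are untouched. Because DOR is exploratory, this is a correction worth making for its small cost, and it does not threaten the trial's main conclusions.

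The wording of note 11 is a separate matter. It conflicts with Section 2.1, Section 7.1.2.6 and Table 13 on when progression is confirmed. Since that confirmation bears on continuing or stopping treatment, this review says only that the texts must be reconciled.

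**What to change.** In Section 8.4.1, define DOR for subjects with a confirmed CR or PR, dated from the first documentation of the response that is later confirmed. The DOR denominator then equals the ORR numerator. State there, or in Section 7.1.2.6, that the next scheduled 9-weekly scan can confirm a CR or PR. Carry the same definition into the supplemental SAP.

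Separately, have the sponsor reconcile note 11 in both flow charts with Section 2.1, Section 7.1.2.6 and Table 13.

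The DOR change costs one word and a short sentence, with no extra scans if the scheduled scan counts as confirmation. The downside is fewer subjects in the DOR summary whenever some responses go unconfirmed.

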8.4.2 Safety Endpoints

The primary safety endpoint is the rate of DLTs. Safety will be monitored by cumulative data reviews throughout the trial. The toxicities experienced by subjects who have received study treatment, including AEs and SAEs and their grades will be summarized. Other safety measures evaluated in all parts of the study include laboratory safety assessments, ECGs, vital signs, and physical examinations.

A description of safety measures is provided in Section 7.

8.5 Analysis Populations

8.5.1 Safety Analysis Population

The ASaT population will be used for the analysis of safety data in this study. The ASaT population consists of all subjects who received at least 1 dose of study treatment. In case of treatment administration errors, subjects will be analyzed according to the treatment they actually received. For DLT evaluation, ASaT subjects that were observed for safety for 21 days after the first dose of assigned treatment (or 35 days for subjects in optional Arm D) or experienced a DLT prior to 21 days after the first dose of assigned treatment (or prior to 35 days for subjects in optional Arm D) will be included. The replacement subjects will also be considered evaluable if the above specified criteria are met.

At least 1 laboratory or vital sign measurement obtained subsequent to at least 1 dose of study treatment is required for inclusion in the analysis of each specific parameter. To assess change from baseline, a baseline measurement is also required.

8.5.2 Efficacy Analysis Populations

The FAS population will be used for the analysis of efficacy data in this study. It consists of all subjects with a baseline scan with measurable disease by investigator assessment who were administered a dose of the study medicine.

8.6 Statistical Methods

This section describes the statistical methods that address the primary and secondary objectives. Methods related to exploratory endpoints will be described in the sSAP.

PK will be analyzed and reported separately.

8.6.1 Statistical Methods for Efficacy Analyses

Objective response rate will be estimated using an exact method based on the binomial distribution (Clopper-Pearson interval).

8.6.2 Statistical Methods for Safety Analyses

Safety and tolerability will be assessed by clinical review of all relevant parameters including AEs, SAEs, laboratory tests, vital signs, ECG measurements, and physical examinations.

Adverse events will be summarized as counts and frequencies for each dose level. Laboratory tests, vital signs, and other safety endpoints will be summarized as appropriate.

Dose-limiting toxicities will be listed, and further summarized by dose level. The pool adjacent-violators-algorithm [1], which forces the DLT rate estimates to be non-decreasing with increasing dose levels and pools adjacent violators for weighted estimates by sample size, will be used to estimate the DLT rates across doses. The estimates of the DLT rates among subjects treated at the MTD and the 80% Bayesian credible intervals based on a prior distribution of Beta (1,1) for the estimates will be provided.

8.6.3 Summaries of Baseline Characteristics, Demographics, and Other Analyses

Demographic variables, baseline characteristics, primary and secondary diagnoses, and prior and concomitant therapies will be summarized.

8.7 Interim Analyses

In this study there will be no formal hypothesis testing, although an interim analysis may be conducted to enable future trial planning at the Sponsor's discretion and data will be examined on a continuous basis to allow for dose escalation and confirmation decisions.

An interim futility check will be performed for Part 2. If there are no responders among approximately the first 18 evaluable subjects that have at least 1 postbaseline scan assessment, the trial may be stopped early for futility. If the true response rate is 10%, there is an 85% chance to observe at least one responder among 18 subjects.

8.8 Multiplicity

There will be no multiplicity control in this study.

8.9 Sample Size and Power Calculations

Part 1 dose escalation and confirmation is expected to enroll up to approximately 142 subjects (up to 14 subjects per dose level). The final sample size for Part 1 will depend on the number of subjects experiencing DLTs at each dose level, and may be increased if the RP2D is not reached and additional dose levels are required.

For Part 2, the planned sample size is up to approximately 40 subjects. The primary efficacy endpoint will be the ORR based on the investigator assessment per RECIST 1.1. [Table 11](#) shows the ORR estimate and 95% CI under various scenarios. Of note, any \geq second line advanced non-MSI-H/dMMR CRC subjects enrolled in Part 1 and treated at the dose level that is selected for Part 2 will also be included for this efficacy analysis.

Table 11 Estimate and 95% CI of ORR Under Various Scenarios

Sample Size	Number of Responses (PR/CR)	Observed ORR	95% Confidence Interval of ORR
40	4	10%	(2.8%, 23.7%)
	5	12.5%	(4.2%, 26.8%)
	6	15%	(5.7%, 29.8%)
	7	17.5%	(7.3%, 32.8%)
	8	20%	(9.1%, 35.7%)
	9	22.5%	(10.8%, 38.4%)
	10	25%	(12.7%, 41.2%)
54	4	7.4%	(2.1%, 17.9%)
	5	9.3%	(3.1%, 20.3%)
	6	11.1%	(4.2%, 22.6%)
	7	13.0%	(5.4%, 24.9%)
	8	14.8%	(6.6%, 27.1%)
	9	16.7%	(7.9%, 29.3%)
	10	18.5%	(9.3%, 31.4%)
It is assumed that: 1) $40 \geq$ second line advanced non-MSI-H/dMMR CRC subjects are enrolled in Part 2 (expansion) and are also evaluable for efficacy analysis; 2) the number of \geq second line advanced non-MSI-H/dMMR CRC subjects enrolled in Part 1 and treated at the dose level that is selected for Part 2 could be between 0 and 14.			
CR=complete response; CRC=colorectal; ORR=overall response rate; PR=partial response.			

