Under Amendment 3, Arm A is to start at 50 mg bid of MK-8353 and Arm B was added and is to be enrolled in parallel to Arm A. In addition, 2 optional arms, Arm C (in which MK-8353 is to be administered 1 week on/1 week off at a starting dose of 50 mg qd in combination with pembrolizumab), and Arm D (in which MK-8353 is to be administered first as monotherapy during a 2-week run-in at a starting dose of 50 mg qd, and then followed by continuous administration in combination with pembrolizumab at a dose of 50 mg qd). Lower doses of MK-8353 could be implemented in the event of unacceptable toxicities or based on PK measurements in Arm A or Arm B. Doses of MK-8353 at 10 mg and 30 mg could also be explored in Arms C or D (refer to Section 5.2). Additional doses between all described doses may be added based on reported toxicities upon agreement between the investigators and the Sponsor.

Barring dose-limiting toxicities (DLTs), additional subjects are to be enrolled and dose-finding is to proceed, according to an algorithm based on the mTPI method, targeting a dose with a 30% DLT rate for the combination therapy to determine the RP2D. Up to approximately 142 subjects evaluable for safety and tolerability are to be enrolled according to the mTPI method. The final number of subjects enrolled in Part 1 will depend on the empirical safety observations (ie, DLTs), and the dose and schedule ultimately identified as the RP2D using the mTPI design.

In Part 2, up to approximately 40 subjects with advanced non-MSI-H/dMMR CRC, who received at least 1 and up to 5 prior lines of therapy, will be enrolled at the RP2D(s) of the combination treatment in the expansion cohort to further evaluate safety and efficacy. Several doses and schedules of MK-8353 in combination with pembrolizumab may be

explored in separate cohorts in Part 2. Based on previous studies, approximately 50% of enrolled subjects are expected to present with a KRAS mutant MMR proficient CRC. Preliminary efficacy will be evaluated using overall response rate (ORR) assessed by the investigator based on the Response Evaluation Criteria in Solid Tumors version 1.1 (RECIST 1.1) as a secondary objective. The duration of response (DOR), disease control rate (DCR), and progression-free survival (PFS) based on RECIST 1.1 as assessed by the investigator, as well as overall survival (OS) will be also evaluated as exploratory objectives.

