3.2 Secondary Objective(s) & Hypothesis(es)

- (1) **Objective:** To determine 1 or more RP2D of MK-8353 when given in combination with pembrolizumab in subjects with advanced solid tumors.
- (2) **Objective:** To evaluate the antitumor activity (ORR based on RECIST 1.1 as assessed by the investigator) of MK-8353 in combination with pembrolizumab in subjects with advanced solid tumors who received MK-8353 at RP2D in Part 1 and in Part 2.
- (3) **Objective:** To evaluate serum levels of protein biomarkers, such as carcinoembryonic antigen (CEA), CA-125, or CA19-9, before and after

administration of MK-8353 in combination with pembrolizumab in subjects with advanced solid tumors.

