3.3 Exploratory Objectives

- (1) **Objective:** To assess the PK profile of MK-8353 when given in combination with pembrolizumab in subjects with advanced solid tumors and in subjects with \geq second line advanced non-MSI-H/dMMR CRC.
- (2) **Objective:** To evaluate the DOR, DCR, and PFS based on RECIST 1.1 as assessed by the investigator, and OS, in subjects with advanced solid tumors, and in subjects with \geq second line advanced non-MSI-H/dMMR CRC who received MK-8353 at RP2D in combination with pembrolizumab in Part 1 and in Part 2.
- (3) **Objective:** To evaluate the correlation between programmed cell death-ligand 1 (PD-L1) expression levels and tumor response when MK-8353 is given in combination with pembrolizumab in subjects with advanced solid tumors or \geq second line advanced non-MSI-H/dMMR CRC.
- (4) **Objective:** To evaluate the ORR, DOR, DCR, and PFS based on RECIST 1.1 as assessed by the investigator, and OS in 1) subjects with RAS/RAF mutant versus RAS/RAF wild-type with advanced solid tumors or \geq second line advanced non-MSI-H/dMMR CRC; 2) subjects with pMMR versus dMMR advanced solid tumors or \geq second line advanced non-MSI-H/dMMR CRC; and 3) subjects with left versus right advanced non-MSI-H/dMMR CRC who received MK-8353 in combination with pembrolizumab.
- (5) **Objective:** To identify molecular (genomic, metabolic, and/or proteomic) biomarkers that may be indicative of clinical response/resistance, safety, pharmacodynamic activity, and/or the mechanism of action of MK-8353, pembrolizumab, and/or the combination therapy.

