4.2.3 Rationale for Endpoints

4.2.3.1 Efficacy Endpoints

The efficacy of MK-8353 in combination with pembrolizumab will be evaluated in subjects with advanced solid tumors, and in subjects with \geq second line advanced non-MSI-H/dMMR CRC, by measuring ORR, DCR, DOR, PFS, and OS.

Overall response rate will be used as a secondary endpoint as assessed by the investigator based on RECIST 1.1, to evaluate efficacy of MK-8353 in combination with pembrolizumab in subjects with advanced solid tumors, and in subjects with \geq second line advanced non-MSI-H/dMMR CRC.

Radiological images (eg, computed tomography [CT], magnetic resonance imaging [MRI]) will be collected for possible analysis by blinded, independent central review. The Site Imaging Manual (SIM) contains specific instructions for the acquisition and submission of radiologic images to the central imaging vendor for this study.

Exploratory endpoints include OS, DCR, DOR, and PFS as assessed by the investigator based on RECIST 1.1 (refer to Appendix 12.4).

Secondary and exploratory efficacy endpoints will also be summarized according to RAS/RAF mutant status, pMMR status, and colon side of the tumors (in subjects with non-MSI-H/dMMR CRC).

Immune-related RECIST could be used by the investigator for treatment decision as outlined in Section 7.1.2.6 and Appendix 12.5.

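### Do objective 3.2(2) and Section 8.9 conflict on the population for the response rate, and does Table 11 mislead if several regimens enter Part 2?

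*Combined protocol and SAP*

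**What the plan says.** Objective 3.2(2) sets ORR "in subjects with advanced solid tumors who received MK-8353 at RP2D in Part 1 and in Part 2", with no restriction by tumor type. Exploratory objective 3.3(2), which covers response duration, disease control, progression-free and overall survival, names solid tumors and also "CRC who received MK-8353 at RP2D in combination with pembrolizumab in Part 1 and in Part 2". Section 4.2.3.1 uses ORR "to evaluate efficacy of MK-8353 in combination with pembrolizumab in subjects with advanced solid tumors, and in subjects with" second-line-or-later CRC, so it names both populations for this endpoint.

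In the analysis part, Section 8.5.2 defines the full analysis set (FAS) as "all subjects with a baseline scan with measurable disease by investigator assessment who were administered a dose of the study medicine", without restriction by tumor, dose or part. Section 8.6.1 gives only the exact Clopper-Pearson method. Section 8.9 calls ORR the primary efficacy endpoint for Part 2 and states that eligible CRC subjects "enrolled in Part 1 and treated at the dose level that is selected for Part 2 will also be included". The Table 11 footnote assumes that the number of such Part 1 subjects "treated at the dose level that is selected for Part 2 could be between 0 and 14".

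Section 2.1 allows several doses and schedules to be "explored in separate cohorts in Part 2", with a futility check in each cohort. Sections 5.2 and 5.3 provide for random assignment in that case.

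**The concern.** Section 8.1 lists ORR as the key secondary endpoint, and it is the trial's main readout of activity. A reader expects the objective and the analysis section to describe the same subjects, and on their face they do not. Part 1 admits any solid tumor and does not select on MSI status. Read literally, objective 3.2(2) could therefore place dMMR or non-CRC subjects beside the Part 2 CRC subjects. Section 4.1.3.2 cites response rates to pembrolizumab alone of 40% in dMMR CRC, 71% in dMMR non-CRC and 0% in pMMR CRC, so tumor mix could move the estimate. In an open-label trial, an unranked choice of population might also be made after responses are known.

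The second worry is precision. Table 11 shows only N = 40 and N = 54 and speaks of one selected dose level. If the roughly 40 Part 2 subjects are split over regimens, each regimen's interval is wider than any comparable row in the table.

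**Working it through.** **Reproducing Table 11.** For x responders among n, the Clopper-Pearson 95% limits are: lower = 2.5% quantile of Beta(x, n-x+1); upper = 97.5% quantile of Beta(x+1, n-x). The larger N is 40 + 14 = 54, one dose level at its maximum of 14 (Section 5.2.1.2). All 14 rows reproduce, apart from two upper limits that differ by 0.1 point: 8/40 computes to 35.65% (just below, so 35.6; printed 35.7) and 9/40 to 38.45% (just above, so 38.5; printed 38.4). The futility statement in Section 8.7 also holds: 1 - 0.9^18 = 0.850.

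**How far the two populations can differ.** Assume 4/40 respond in Part 2 and 14 Part 1 subjects were treated at the selected dose, with 0 to 2 responders, none of them CRC.

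| Set | Responders/N | ORR | 95% interval | Width (points) |
|---|---|---|---|---|
| 3.2(2), no Part 1 responder | 4/54 | 7.4% | 2.1 to 17.9 | 15.8 |
| 3.2(2), two Part 1 responders | 6/54 | 11.1% | 4.2 to 22.6 | 18.4 |
| 8.9, none of the 14 eligible CRC | 4/40 | 10.0% | 2.8 to 23.7 | 20.9 |
| 8.9, seven of the 14 eligible CRC | 4/47 | 8.5% | 2.4 to 20.4 | 18.0 |

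Differences, 3.2(2) minus 8.9:
- No eligible CRC in Part 1: 7.4 - 10.0 = -2.6 and 11.1 - 10.0 = +1.1.
- Seven eligible CRC: 7.4 - 8.5 = -1.1 and 11.1 - 8.5 = +2.6.
- All 14 eligible CRC: the sets coincide.

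The result depends on the assumed responders. In an extreme case, 7 of the 14 respond and none is CRC: 11/54 = 20.4% (10.6 to 33.5) against 4/40 = 10.0%, a gap of 10.4 points. A gap of that kind would not stay hidden. Section 4.2.3.1 summarizes secondary endpoints by pMMR status without condition, and objective 3.3(4) lists ORR in pMMR versus dMMR subjects. Section 8.10's as-needed wording is not the only provision.

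**Several regimens.** A futility check at about 18 per cohort fits two cohorts within 40 subjects (2 × 18 = 36) but not three (3 × 18 = 54), so two is the natural case. The allocation ratio is not stated; assume 20 + 20. With 0 to 14 Part 1 CRC subjects added to each, N per regimen is 20 to 34.
- 2/20 = 10.0%, interval 1.2 to 31.7, width 30.5.
- 3/34 = 8.8%, interval 1.9 to 23.7, width 21.8.
- For comparison, 4/40 has width 20.9 and 5/54 has 17.2.

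**Setting the provisions side by side.** Section 8 opens by stating that it holds the primary and key secondary analyses. Within it, 8.9 is the only place that says which subjects, beyond FAS membership, enter the Part 2 efficacy analysis, and it names the CRC set. CRC is a solid tumor, so that set lies inside the population of objective 3.2(2). The objective mentions both parts but does not say that they are pooled across tumor types. Separate cohorts, a futility check in each and random assignment all lead an analyst to estimate ORR per regimen.

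**The case for a change.** The strongest case for a change is that Section 8 reserves key secondary analyses to itself and leaves only exploratory and nonconfirmatory ones to the supplemental plan, so the gap cannot properly be settled there. Calling ORR the primary efficacy endpoint ranks the endpoint, not its population. Objective 3.3(2) names both populations while 3.2(2) names one, so the drafting is uneven even within Section 3.

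These observations are correct. No sentence expressly labels the key ORR population or states per-regimen estimation, and a clarifying line in 8.6.1 would be tidier. What does not stand is that the result would be wrong or open to silent selection. Section 8.9 already commits to the CRC set in writing. Both sets are well defined and contain named subjects, and each estimate would carry its own denominator.

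The larger repairs carry costs. Aligning 8.5.2 on a single ORR population would narrow the FAS that serves all efficacy data, including the objective 3.3(4) comparisons, which are not limited to the recommended dose. Rewriting a key secondary objective needs an amendment. Section 8.7 has data examined continuously, so a redefinition made now, after Amendment 07, could be influenced by Part 1 responses already seen. Extra rows in Table 11 would show lower precision but alter no sample size and no decision.

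**Conclusion.** The difference in wording is real, but it is a gap that analysts would fill sensibly, not an error in the plan. The CRC set in 8.9 serves as the main activity estimate, the wider solid-tumor summary stands beside it with the planned breakdown by mismatch-repair status, and ORR is reported per regimen if more than one is expanded.

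Under the main illustration the choice of set moves ORR by at most 2.6 points, within intervals about 16 to 21 points wide. That rests on 4/40 responders in Part 2 and 0 to 2 non-CRC responders among 14 Part 1 subjects; a larger gap needs many non-CRC responders. Sections 8.7 and 8.8 provide for no hypothesis test and no multiplicity control, and the futility rule counts zero responders rather than using the interval. Table 11 is correct for the single dose level its footnote assumes. Two regimens of 20 would widen the interval at an observed 10% from 20.9 to 30.5 points, which readers should bear in mind but which calls for no change.
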